After the informed consent form is signed, the screening tests are performed and the compliance with the inclusion / non-inclusion criteria is evaluated. The patient who passed the screening tests is enrolled in the study.¹

Clinical phase

Patients enrolled in the study receive Bioven at a dose of:

0.8-1.0 g / kg intravenously once a day for 2 consecutive days, the course dose is 1.6-2.0 g / kg. Allowed repeat course at same dosage in period 14-28 days from first infusion, if required.

The CRF records the time of administration of the study drug, the occurrence of possible adverse events.

Prescribed therapy and diagnostic results are recorded in the CRF based on the primary documentation.

Data are entered into the CRF according to the patient management plan.

Follow-up phase and completion of the study

This stage lasts for 4 weeks after the last administration of the drug (possible repeat course is not considered).

In all patients, the platelet count will be determined 48 hours after the start of the first administration of the study drug, on the 7th (\pm 1 day), 14th (\pm 2 days), 21st (\pm 3 days), 28th (+ 1-3 days) days after the start of therapy.

The results of the study are evaluated by endpoints.

Phase-by-phase breakdown and breakdown of visits are detailed in Section 6.4 "Tabulated schedule of events". Information is entered into the CRF after each visit, according to the "Schedule of study events".

The decision on any examinations and diagnostic procedures in routine clinical practice is made and controlled by professionals.

Blood sampling for platelet count is performed 6 times:

- at the screening phase;
- 48 (\pm 3) hours after the start of study drug administration;
- on the 7th (± 1) day from the start of study drug administration;
- on the 14th (± 2) day from the start of study drug administration;
- on the 21st (± 3) day from the start of study drug administration;
- on the 28th (+ 1-3) day from the start of study drug administration.

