The time of each blood draw and the start time of drug administration should be recorded; during each administration of the drug, it is necessary to evaluate the physical data, such as heart rate, blood pressure, body temperature, respiratory rate, and the severity of hemorrhagic syndrome. Patients' serum samples should be stored frozen at the temperature of -65 - -85 ° C (second aliquot) to ensure the possibility of performing repeat laboratory tests if necessary, in the future. The study involves scheduled visits of patients to the doctor:

1st visit (Day -14 – Day -1) – the patients are screened, checked for compliance with the criteria of inclusion / non-inclusion (exclusion), enrolled in the study;

2nd visit (Day 0 - Day +1 – Day +2) – hospitalization, administration of the study drug for 2 days, physical examination, assessment of the status of hemorrhagic syndrome, blood sampling to determine platelet count, manual platelet counts, Coombs test, Total IgG levels (g/l);

¹ Due to the variability in PLT levels in patients with chronic immune thrombocytopenia (wave-like), it is possible to re-screen or extend the duration of the screening stage, but only if the study subject meets all other specified inclusion criteria, does not have non-inclusion and exclusion criteria.

| Bioven | |
|----------------------------|--|
| Trial Code: 2021-BV-ITP-BP | |

3rd visit (Day $+7 \pm 1$ day) – physical examination, assessment of the status of hemorrhagic syndrome, blood sampling to determine platelet count, manual platelet counts, Coombs test in case hemolysis was detected during the previous visit (according to the laboratory data);

4th visit (Day $+14 \pm 2$ days) – physical examination, assessment of the status of the hemorrhagic syndrome, blood sampling to determine platelet count, manual platelet counts, Coombs test in case hemolysis was detected during the previous visit (according to the laboratory data).

If a decrease of platelets count $< 30 \times 10^9/L$ was recorded, then approximately a day after the visit, an additional blood test is performed with a platelet count.

This visit can be performed by telephone / video, provided that the patient's status can be adequately assessed and biomaterials for laboratory tests can be sampled in Local Laboratory or at the collection point of the or Central Laboratory designated by the Sponsor;

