5. SELECTION AND EXCLUSION OF RESEARCH SUBJECTS

5.1. Inclusion criteria

- Signed Informed consent form to participate in the study;
- Men and women aged 18-65 years;
- Significantly confirmed chronic primary ITP (at last 12 months after diagnosis);
- The general analysis of blood should be normal except for the isolated thrombocytopenia. Patients with low hemoglobin (but above 90 g / l) may be included if there are symptoms of bleeding;
- In case of diagnosis of bleeding symptoms, reticulocyte counts should be monitored;
- Platelet count $< 30 \times 109/L$;
- If the patient is taking corticosteroids, the treatment regimen / dose should be stable (at least 2 weeks before screening);
- Negative pregnancy test (in women of reproductive age), willingness to use reliable methods of contraception throughout the study;
- The results of physical, instrumental and laboratory examination of patients within the norm and deviations are considered by the investigator as clinically insignificant;
- The ability, according to the investigator, to follow all the requirements of the study protocol.

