- Patient's wish
- Occurrence of severe and/or unexpected AE/AR in patient during the study, that require discontinuation of the drug;
- The need to prescribe drugs prohibited in this study.
- Significant deterioration of the patient's condition during the study period;
- Failure of the patient to adhere to the treatment regimen;
- Failure of the patient to follow the procedures established under the protocol;

Due to the variability of PLT levels in patients with chronic immune thrombocytopenia (wave), it is possible to re-screen or extend the duration of the screening phase, but only if the subject meets all other specified inclusion criteria and has no inclusion or exclusion criteria.

Patients who drop out at the screening stage are not included in the efficacy and safety analysis, as they do not receive any doses of the investigational drug (ID).

Patients who do not receive a full course of study drug are included in the safety analysis but not in the efficacy analysis.

Patients who dropped out of the study after completion of SD administration during the followup period are considered in the efficacy and safety analysis. The data of such patients are evaluated by parameters that can be analyzed at a certain point in time. The dropped data are not analyzed.

For all patients who complete the study due to AE, requiring discontinuation of treatment with the studied drugs, it is necessary to conduct the procedures of the final visit in the near future after the development of AE. After stopping treatment, the patient should be monitored until the reaction disappears or its clinically significant signs. Patients who received at least 1 dose of SD but prematurely dropped out of the study are included by the investigator in the analysis of tolerability of the study drug.

The reasons for premature withdrawal from the study are indicated in the Individual registration form.

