10 STATISTICS

10.1 Content of statistical analysis

The null hypothesis for the primary efficacy endpoint H0: $p-p_0 \leq \delta$, where clinical effectiveness p is the proportion of patients who responded to therapy with the study drug BIOVEN; p_0 - proportion of patients responding to therapy according to literature data: δ - the limit of the difference of proportions without clinical significance. An alternative hypothesis H1: $p-p_0 > \delta$ («non-inferiority study» according to the guideline EMA «Points to consider on switching between superiority and non-inferiority» CPMP/EWP/482/99, London, 27 July 2000 Ta EMA "ICH Topic E 9 Statistical Principles for Clinical Trials" CPMP/ICH/363/96).

According to the EU recommendations on clinical studies of immunoglobulin normal for intravenous administration (Guideline on the clinical investigation of human normal immunoglobulin for intravenous administration (IVIg), EMA/CHMP/BPWP/94033/2007 rev. 3, 28 June 2018) the obtained results will be compared with literature data.

To test the null hypothesis, a two-tailed test will be used, based on the principles of estimating a 95% confidence interval for the difference in proportions and comparing it with the lower limit of equivalence (at a significance level of α 5%). For non-inferiority research, the null hypothesis is rejected if the conditions are met:

$$\sqrt{n(p-p_0-\delta) / p^{(1-p^{-})} > z_{\alpha/2}}$$

or
 $(p-p_0-\delta) / \sqrt{(\frac{p(1-p)}{n} + \frac{p_0(1-p_0)}{n_0})} > z_{\alpha/2}$

Confidence intervals of the difference will be calculated according to the generally accepted Wald method:

$$(p_1 - p_2) \pm z_{\alpha/2}^* \sqrt{(\frac{p_1(1 - p_1)}{n_1} + \frac{p_2(1 - p_2)}{n_2})}$$

The number of patients for the portion taken from literature sources is taken from the 2020 publication and will be 82 [Parodi E, Russo G, Farruggia P, Notarangelo LD, Giraudo MT, Nardi M, et al. Management strategies for newly diagnosed immune thrombocytopenia in Italian AIEOP Centres: do we overtreat? Data from a multicentre, prospective cohort study. Blood Transfus. 2020;18(5):396.]

Methods of descriptive statistics (for categorical variables - number and part in %, for quantitative variables - n, arithmetic mean, median, standard deviation, minimum and maximum), including construction of graphs and charts, methods of interval estimation (calculate of 95% confidence intervals for proportions and differences of fractions).

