C) Quantitative variables of efficiency, which are measured at study entry (T $_{start}$) and at the final visit (T $_{endpoint}$).

Provide indicators of descriptive statistics (n, arithmetic mean, median, standard deviation, minimum and maximum value) for time points T start and T endpoint, and also for differences [T endpoint – T start]. Represent this dynamic graphically.

Calculate for these parameters their relative change in comparison with the initial state/base-line according to the formula:

$$X(\%) = \frac{T endpoint - T start}{T start} * 100,$$

Evaluate the dynamics using the Student's paired test or the Wilcoxon signed rank test, depending on the results of testing the normality of the distribution of differences $[T_{endpoint} - T_{start}]$ using the Shapiro-Wilk test.

D) Evaluation of quantitative variables measured at more than two measurement points.

Specify the indicators of descriptive statistics (n, arithmetic mean, median, standard deviation, minimum and maximum value) for each measurement point, as well as for the differences $[T_i - T_{start}]$, where *i* are subsequent visits. Build a dynamics graph.

Calculate for these parameters their relative change at each subsequent visit in comparison with the initial state according to the formula:

$$X(\%) = \frac{Ti - Tstart}{Tstart} * 100,$$

where *i* is subsequent visits according to the patient examination scheme.

Evaluate the dynamics of changes in quantitative variables using univariate analysis of variance (ANOVA) or rank analysis depending on the normality of the distribution, which is tested using the Shapiro-Wilk test. At the same time, the dependent variable is the analyzed parameter, the "visit" factor is a fixed parameter. To assess the magnitude and significance of the difference between visits using contrast analysis (simple contrasts) or post hoc analysis using Tukey's test (for ANOVA) or Wilcoxon signed rank test with Holm's correction (for rank test). To verify the prerequisites for the application of variance analysis, a check of the normality of the distribution of residuals will be
| Bioven | Page 73 |
|----------------------------|--------------------------------|
| Trial Code: 2021-BV-ITP-BP | Version 1.4 from July 03, 2023 |

performed using the Shapiro-Wilk test. In the event that the balances are not normally distributed, an appropriate rank analysis will be performed. Make statistical conclusions.

triate substear conclusions.

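### Mean percent change in platelets from each patient's own baseline drifts upward when counts merely fluctuate and overweights the lowest baselines; report fold change instead

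*Combined protocol and SAP*

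**What the plan says.** Section 10.3.3 C covers quantitative efficacy variables measured at entry and at the final visit: "Calculate for these parameters their relative change in comparison with the initial state/base-line according to the formula", followed by X(%) = (Tendpoint - Tstart)/Tstart x 100. Part D covers variables measured at more than two points and uses the same form at every later visit: "Calculate for these parameters their relative change at each subsequent visit in comparison with the initial state according to the formula".

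Neither part names platelets. The Synopsis, however, says "Blood sampling for platelet count is performed 6 times": at screening, at 48 hours and around days 7, 14, 21 and 28. In that list and in the section 6.4 schedule, screening is the only pre-dose count, so it serves as Tstart. The inclusion criteria (Synopsis and section 5.1) require a count below 30 x 10^9/L and set no lower limit. Section 5.3 adds: "Due to the variability of PLT levels in patients with chronic immune thrombocytopenia (wave), it is possible to re-screen".

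On summaries, part D asks: "Specify the indicators of descriptive statistics (n, arithmetic mean, median, standard deviation, minimum and maximum value) for each measurement point", and the same for the absolute differences from baseline. For X(%) it says only that it is to be calculated. The general rule in section 10.1 fills the gap: "for quantitative variables - n, arithmetic mean, median, standard deviation, minimum and maximum".

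**The concern.** A ratio with a small, noisy denominator is awkward to average. A fall cannot go beyond -100% but a rise has no ceiling, so ups and downs that cancel on the absolute or log scale do not cancel in X(%). The denominator here is a count that must be under 30, may be 1 or 2, and is described by the protocol as varying in waves. If it is 0, X(%) is undefined, and the plan gives no rule for that.

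What is at stake is how the platelet rise by visit is described in an uncontrolled trial. A mean percent rise reported for each visit could sit well above what the typical patient experienced and would depend heavily on how many very low baselines were enrolled.

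**Working it through.** The documents state no figure for percent change, so there is none to reproduce. The group size of 36 is the planned number in section 10.2. The platelet distributions below are assumptions and are marked as such.

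**1. Asymmetry (exact).** Two patients go 10 to 20 and 20 to 10. Mean absolute change = (10 - 10)/2 = 0. Geometric mean ratio = sqrt(2 x 0.5) = 1. Mean X = (+100% - 50%)/2 = +25%.

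**2. Expected drift with no drug effect.** Take baseline and follow-up as independent lognormal readings around the same patient level, with within-patient log SD s. Then E[Ti/Tstart] = exp(s^2), so E[X] = exp(s^2) - 1. The documents give no s; assumed values:
- s = 0.2: exp(0.04) - 1 = +4%
- s = 0.3: exp(0.09) - 1 = +9%
- s = 0.5: exp(0.25) - 1 = +28%
- s = 0: exactly 0

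A simulation of 29 patients in an unchanged group agrees. It assumed lognormal patient levels with median 12 or 18, between-patient log SD 0.6, within-patient CV 20% to 50%, and all counts below 30. Mean X was +4% to +21%, while median X was 0.2% to 0.9%, the geometric mean change 0.2% to 0.6% and the mean absolute change about 0. The six lowest baselines supplied 74% to 89% of the total.

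**3. Weight of low baselines (exact).** Contribution of one patient to the mean of 36, each ending at 101:
- from 1: (100/1) x 100/36 = 278 points
- from 2: (99/2) x 100/36 = 138 points
- from 25: (76/25) x 100/36 = 8 points

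**4. With a real response (illustration).** Assumed: whole-number baselines uniform on 1 to 29; 78% responders with median count 100 and log SD 0.6; the rest fluctuating around baseline with log SD 0.3.
- Mean X = 0.78 x (100 x exp(0.18) x E[1/b] - 1) + 0.22 x (exp(0.045) - 1). With E[1/b] = 0.1366 this is about 1,199%.
- Geometric mean ratio = exp(0.78 x (ln 100 - E[ln b])). With E[ln b] = 2.457 this is 5.34, a rise of 434%.
- The typical trial median of X, by simulation, is about 450%.
- With the lowest baseline at 5 instead of 1, E[1/b] = 0.0751 and E[ln b] = 2.723. Mean X falls to about 625%, while the ratio falls only to 4.34.

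Under other assumed response patterns (a common rise of 50, or a rise to a level around 80), the six lowest of 29 baselines supplied 32% to 47% of the percent total, against 21% to 23% of the absolute total.

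**5. Selection.** If only the baseline is required to be below 30, as in this trial, regression to the mean comes on top. With no drug effect, simulated mean X was +5% to +40% and the absolute mean rose by 0.3 to 3.8. Across the assumptions tried, the geometric mean ratio was still about 1% to 23% above 1.

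**The case against.** The strongest reply is that X(%) carries little weight in this plan. It is not among the endpoints in sections 8.1 and 8.2. The tests in part C use the absolute differences and those in part D use the parameter itself, with a rank fallback. The non-inferiority conclusion in section 10.3.7 rests on R alone. Parts C and D are generic text that never names platelets and attaches no mean or SD to X(%); a mean comes in only through section 10.1, which brings the median with it. All of this stands. It limits the consequence to description.

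It is also fair that the size of the drift depends on variability the documents do not report, and that reporting the median and range of X(%) would remove most of the skew without changing scale. What remains is that the plan orders this quantity at every visit, and that printing a median beside the mean does not correct the mean.

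A reader might further infer that a confidence interval for mean percent change would be unreliable. The interval methods in section 10.1 are for proportions and their differences, and the intervals in 10.3.3 B are for variables assessed once at the final visit. No interval is specified for X(%), so there is none to criticise.

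**Conclusion.** The point holds as a limited improvement to the descriptive analysis. Applied to platelets, the arithmetic mean of X(%) is biased upward in expectation when counts fluctuate: about +4% to +28% with no drug effect at assumed log SDs of 0.2 to 0.5, before selection. It also gives excess weight to the lowest baselines. The direction follows from the formula and from the protocol's own account of fluctuating counts; the size rests on the assumed SDs. That X(%) will be applied to platelets and averaged is a reasonable reading, not an explicit instruction.

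Three stronger readings are not supported:
- That the efficacy conclusion is biased by this formula. The responder analysis and the non-inferiority comparison do not use X(%).
- That a handful of patients would make up most of the reported rise. With a real response the lowest baselines have disproportionate weight, but in the scenarios run with 29 patients the lowest six stayed below half of the total.
- That changing scale removes all spurious rise. Selection at a count below 30, with re-screening allowed, leaves regression to the mean in absolute change and fold change alike, and there is no control group to measure it.

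**What to change.** In section 10.3.3 C and D, for platelet count:

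- Replace a mean of X(%) by an analysis of ln(Ti/Tstart). At each visit report the geometric mean ratio to baseline (fold change) with its back-transformed 95% CI, plus the median and range of the ratio.
- Keep the absolute differences as planned.
- State in advance how a recorded count of 0 is handled at any visit, for example by setting it to the lowest reportable value, since neither X(%) from a zero baseline nor a log ratio is defined there.
- State in the report that selecting counts below 30 x 10^9/L, with re-screening, leaves some regression to the mean on any scale.

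Fold change also matches the two-fold criterion already built into R. The cost is SAP wording only: same data, no added procedures. The reported rise will look smaller than a mean percent change.

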For variables that are "time to event" survival curves will be constructed in each group using the Kaplan-Meier method, median survival will be estimated, and group comparisons will be made using the log-rank test. If the survival curves intersect, then Cox regression will be used to compare the groups according to these variables.

| Bioven | Page 69 |
|----------------------------|--------------------------------|
| Trial Code: 2021-BV-ITP-BP | Version 1.4 from July 03, 2023 |

To evaluate the significance in the dynamics in the case of evaluating the parameter on two visits (before and after):

- To assess the dynamics of quantitative variables, the Student's test for paired data or the Wilcoxon signed rank test will be applied, depending on the results of testing the normality of the distribution of differences [after - before] using the Shapiro-Wilk test.

- To assess the dynamics of categorical variables in groups, the McNemar criterion or the criterion of homogeneity of marginal frequencies will be applied, depending on the number of categories.

- To assess the statistical significance of differences in categorical variables in unrelated groups, Pearson's chi-square or Fisher's exact test will be applied (depending on the frequency distribution in table 2*2).

To evaluate the dynamics in the case of measuring variables on more than two visits, methods of univariate analysis of variance (ANOVA) will be used followed by contrast analysis (simple contrasts) or a posteriori analysis using Tukey's test. Analysis of covariance (ANCOVA) will be used to compare those variables for which the data were heterogeneous at baseline.

To verify the prerequisites for the application of variance and covariance analyses, a check of the normality of the data distribution and their residuals will be performed using the Shapiro-Wilk test. If the residuals are not normally distributed, or if the data fail the normality test, an appropriate rank analysis will be performed.

For the Shapiro-Wilk test, the significance level will be 0.01, and for other criteria - 0.05. In the event of the effect of multiple comparisons, an adjustment of the level of significance will be applied using the Holm method or the Benjamini-Hochberg method.

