10.3.3. Analysis of effectiveness

Additional information about the statistical model for evaluating the effectiveness of the drug by the main variable is given in Section 10.1. "The content of statistical analysis".

A) The primary outcome of efficiency – Proportion (%) of patients with response (R).

Primary efficiency variable – achievement of R during the study. *R is defined according to criteria* *:

| Bioven | Page 71 |
|----------------------------|--------------------------------|
| Trial Code: 2021-BV-ITP-BP | Version 1.4 from July 03, 2023 |

- Patients with R: the number of platelets > $30x10^{9}/l$ and at least a two-fold increase from the baseline count. This must be confirmed by at least 2 blood tests performed once every 7 days and the absence of bleeding;

The categories of the variable will be defined as "Yes" or "No" respectively.

* The criteria are defined according to the Guideline on the clinical investigation of human normal immunoglobulin for intravenous administration (IVIg), EMA/CHMP/BPWP/94033/2007 rev. 4, 16 December 2021 as well as according to the criteria of the international working group on ITP in 2009. (Rodeghiero, F., Stasi, R., Gernsheimer, T., Michel, M., Provan, D., Arnold, D. M., ... & George, J. N. (2009). Standardization of terminology, definitions, and outcome criteria in immune thrombocytopenic purpura of adults and children: report from an international working group. Blood, The Journal of the American Society of Hematology, 113(11), 2386-2393.);

B) Secondary effectiveness variables.

For variables assessed once at the final visit, descriptive statistics methods will be used to describe these variables (for quantitative parameters - n, arithmetic mean, median, standard deviation, minimum and maximum value; for categorical parameters - number and share in %). 95% confidence intervals will be calculated. In the case of measuring variables at more than two visits, one-way analysis of variance (ANOVA) methods will be used.

Censored data will be analyzed using the Kaplan-Meier method or the log-rank test.

Secondary efficacy endpoints are transformed into corresponding efficacy variables:

Achieving a complete response (CR) during the study.

CR is determined according to the criteria *:

 Patients with CR: platelets count > 100 x 10⁹/L, which is confirmed by 2 blood tests performed at least 7 days apart and the absence of bleeding;

The categories of the variable will be defined as "Yes" or "No" respectively.

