10.3.4. Analysis of safety and tolerability parameters

A) Data on AE/AR, Indicators of descriptive statistics (frequency and part in percent) and a list of adverse reactions according to the MeDRA classification

B) Data on SAE. Indicators of descriptive statistics (frequency and part in percent) and a list of adverse reactions according to the MeDRA classification.

Clinically significant deviations in indicators characterizing the safety and tolerability of the drug: Laboratory results of general blood analysis, biochemical blood analysis and general urinalysis; the result of determining the Coombs test and signs of hemolysis.

Provide descriptive statistics for these indicators (n, arithmetic mean, median, standard deviation, minimum and maximum value) for all visits.

To evaluate the dynamics of laboratory indicators, we used the Student's test for paired data or the Wilcoxon signed rank test, depending on the normality of the distribution of paired differences ["after" - "before"]. Create dichotomous variables with the categories "normal" and "abnormal", calculate the indicators of descriptive statistics (frequency and part in %) for these variables.

Measurement results of heart rate, blood pressure, respiratory rate, body temperature. Indicators of descriptive statistics (n, arithmetic mean, median, standard deviation, minimum and maximum value) for each visit in accordance with the patient examination scheme. Evaluate the trend of changing these parameters.

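### The ANOVA planned for efficacy variables measured at more than two visits has no patient term, so its visit tests use the wrong error term; the fault is confined to this supportive analysis

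*Combined protocol and SAP*

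**What the plan says.** Section 10.3.3 B, on secondary effectiveness variables, states: "In the case of measuring variables at more than two visits, one-way analysis of variance (ANOVA) methods will be used". Section 10.3.3 D gives the rule for more than two measurement points: "Evaluate the dynamics of changes in quantitative variables using univariate analysis of variance (ANOVA) or rank analysis depending on the normality of the distribution". It describes the model as follows: "the dependent variable is the analyzed parameter, the 'visit' factor is a fixed parameter". Differences between visits are then judged by simple contrasts or Tukey's test if the ANOVA is used, and by Holm-adjusted Wilcoxon signed-rank tests if the rank analysis is used. Shapiro-Wilk at the 0.01 level (section 10.3.5) decides between the two. Section 10.1 gives the same general rule ("univariate analysis of variance (ANOVA) will be used followed by contrast analysis"), and so does the synopsis under its statistical methods.

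No section names a patient factor, a random effect, a repeated-measures ANOVA, a covariance structure or a sphericity check.

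Pairing is specified elsewhere. For two time points, section 10.3.3 C says: "Evaluate the dynamics using the Student's paired test or the Wilcoxon signed rank test". For safety laboratory values, section 10.3.4 says: "we used the Student's test for paired data or the Wilcoxon signed rank test, depending on the normality of the distribution of paired differences".

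The trial has one group (section 4.1), and the synopsis schedules six platelet samples per patient.

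**The concern.** One-way ANOVA and Tukey's test assume independent observations. Here each patient contributes up to six values of the same variable, and every comparison between visits is a within-patient comparison. A model with visit alone treats the values as if they came from different people, and stable differences between patients go into the residual.

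Section 10.3.3 D is also uneven within itself. The normality check decides not only between means and ranks but also between unpaired and paired follow-up tests, and there is no statistical reason for that second switch.

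At stake are the p-values and intervals that the report would attach to changes between visits in any quantitative efficacy variable that stays in the ANOVA branch.

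**Working it through.** **Inputs from the documents.** Six measurements per patient (synopsis); one group (section 4.1); significance level 0.05 for tests other than Shapiro-Wilk (section 10.3.5); minimum sample size 29 (section 10.2). The last figure reproduces: (1.96 + 1.28)² × 0.78 × 0.22 / 0.25² = 28.82, rounded up to 29. The plan gives no operating characteristics for the ANOVA.

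**Assumed inputs.** The within-patient correlation ρ is not given, so 0.3, 0.5 and 0.7 are used. SDs by visit are not given either; the main case takes equal variances and equal correlation between all visits.

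**Formula.** Let σ_b² and σ_w² be the between- and within-patient variances, with ρ = σ_b² / (σ_b² + σ_w²). With no true visit effect:
- the visit mean square has expectation σ_w²;
- the one-way residual mean square has expectation σ_w² + σ_b² (very nearly).

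So F is too small by a factor of about 1 − ρ, and the standard error of a visit contrast is too large by 1/√(1 − ρ): 1/√0.7 = 1.20, 1/√0.5 = 1.41, 1/√0.3 = 1.83.

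**Analytic check of the contrast error.** The one-way residual has 29 × 6 − 6 = 168 degrees of freedom, with critical t = 1.974. The actual two-sided error is about 2[1 − Φ(1.974/√(1 − ρ))], which gives 1.8%, 0.5% and below 0.1%. Simulation comes out slightly higher, because the residual mean square itself varies.

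**Simulation, n = 29, six visits, equal variances.** Contrast rows compare one visit with baseline; the power row uses the last visit.

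| | ρ = 0.3 | ρ = 0.5 | ρ = 0.7 |
|---|---|---|---|
| Actual error of a nominal 5% contrast, no patient term | 2.0% | 0.6–0.8% | 0.1% |
| Same, with patient term | about 5% | about 5% | about 5% |
| Power for a 0.5 SD change, no patient term | 47% | 47% | 46% |
| Same, with patient term | 62% | 76% | 93% |
| Actual error of the overall visit test, no patient term | 0.8% | 0.1% | <0.1% |

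The range at ρ = 0.5 is variation between separate simulations; a run of 200,000 trials gives 0.7%. The null results are practically the same at n = 36 and n = 40.

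**Unequal variances.** With illustrative SDs of 8, 60, 90, 60, 35 and 25 from baseline to day 28, the one-way contrast of the most variable visit (day 7) against baseline has an actual error of about 8% to 10%. The other contrasts lie between 0 and 1.6%. The excess at day 7 is present even at ρ = 0 (10.2%), so it comes from pooling unequal variances. A random patient effect alone would not remove it.

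**The case against.** The strongest reply is that little in the trial depends on this analysis, and most of that reply stands.

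- **Endpoints.** The primary endpoint is binary (section 8.1). The listed secondary endpoints are binary, or times and durations (section 8.2), analysed as proportions or by Kaplan-Meier. Section 10.3.3 D names no variable; platelet count is the obvious candidate, but that is an inference.
- **Safety laboratory values.** A reader might infer that all repeated counts are mishandled. Section 10.3.4 does not support this: it sets paired tests for laboratory values, including the general blood test, which contains the platelet count.
- **Rank branch.** A reader might also infer that pairing is always lost once there are more than two visits. It is not, because the rank branch follows up with signed-rank tests. Raw platelet counts would probably go there: entry requires a count below 30 × 10⁹/L, while complete response lies above 100 × 10⁹/L. In a simulation with assumed inputs (29 patients, baseline uniform from 5 to 29, median rises of 2- to 5-fold, log-SD 0.6 or 0.9, correlation 0.3 to 0.7), Shapiro-Wilk rejected normality in at least 99.9% of runs.
- **Missed effects.** The documents do not show that real platelet changes would be missed. With the same assumed rises, the one-way overall test still rejected in at least 97% of runs, and the three earliest post-dose contrasts had 89% to 100% power. Later visits did lose power.

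One part of the reply does not stand. It could be said that the text is merely incomplete and that a within-patient ANOVA was meant. But section 10.3.3 B says one-way, section 10.3.3 D names visit alone, and Tukey's test follows. Where the authors wanted pairing, they wrote it.

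**Conclusion.** The point holds for the ANOVA branch of section 10.3.3 D and for the matching general rule in 10.3.3 B, section 10.1 and the synopsis. Followed as written, that branch gives invalid p-values and intervals for visit differences.

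The direction depends on the variances. With equal variances and positive correlation the tests are conservative, by the amounts tabulated. With unequal variances a single contrast can be too liberal or too conservative, so a flat statement that standard errors are always too large would go too far. All these sizes rest on assumed correlations and SDs, and the 0.5 SD change is hypothetical.

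The non-inferiority conclusion and the sample size do not depend on this analysis. For platelets, the likely remaining gap is that the overall rank test has no name. The rule should be corrected because it is stated wrongly and is cheap to put right, not because a main conclusion is at risk.

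**What to change.** In section 10.3.3 B and D, section 10.1 and the synopsis:

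- Replace the one-way ANOVA by a mixed model for repeated measures, with visit fixed and either a random patient effect or an unstructured covariance over visits. Unstructured is the safer choice where variances differ between visits.
- Analyse platelet counts on the log scale.
- Specify contrasts of each visit against baseline, with the multiplicity adjustment named.
- Name the Friedman test as the overall rank test, and keep the Holm-adjusted signed-rank follow-up tests.

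The cost is SAP wording and standard software. No new data, visits or patients are needed.
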